#### **10.2.1.5 Degree of straining**

The mean degree of straining for an interval will be calculated as the sum of the straining values for the interval divided by the number of BMs recorded within the interval. Change from baseline in the mean degree of straining will be calculated as the post-baseline value minus the baseline value, where baseline is the mean degree of straining recorded during the OIC confirmation period. Negative changes from baseline indicated improvement.

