The study coordinator will review the data in the daily diaries to confirm subject's eligibility for the study. For the purposes of this review, the measurements recorded on the daily diaries can be conveyed by telephone to the study coordinator, or the diaries can be faxed via secure fax, or scanned and conveyed by secure electronic mail, to the research coordinator. If the subject is eligible for randomization, he or she will be asked to return the diaries at the time of the scheduled Visit 2. Patients who do not proceed to Visit 2 or who drop-out of the study at any time may return the diaries by mail.

A minimum of 7 days of diary data must have been recorded before the patient can be randomized for the study. When this is completed, patients who remain eligible and seek to continue with the study will be scheduled for Visit 2 and randomization will be performed. The study coordinator will contact the randomization coordinator at [REDACTED] and obtain the randomized bottle number for the subject. The study coordinator or authorized staff member will dispense a bottle of study medication according to the bottle number provided. Both the patient and the study coordinator will be blind to the contents of the bottle—either naloxegol 25 mg tablets or placebo tablets. The study coordinator also will receive open-label bisacodyl to be used as a rescue laxative.

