### **6.2.4      Bowel movements**

All BMs will be recorded in the diary each day as they occur.

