### **6.2.6 Degree of Straining**

The degree of straining with each BM will be recorded at the time of the BM and after the BSS. A single-item straining question, developed and validated through 1:1 interviews with OIC patients will be asked and recorded in the diary. The question is provided below:

“How much did you strain during your bowel movement?”

Patients will be asked to respond on a 5 point Likert scale on one of the following options:

1=Not at all

2=A little bit

3=A moderate amount

4=A great deal

5=An extreme amount.

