#### **10.2.1.4 Bristol Stool Scale**

The mean daily BSS score for an interval will be calculated as the sum of daily values for the interval divided by the number of days within the interval in which the data were collected. Change from baseline in the mean BSS score will be calculated as the post-baseline value minus the baseline value, where baseline is the mean daily BSS score recorded during the OIC confirmation period. Positive changes from baseline indicate improvement.

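### Mean straining is divided by all recorded BMs, so a recorded BM without a straining rating is scored 0 on a 1-5 scale

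*Combined protocol and SAP*

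**What the plan says.** Section 10.2.1.5 calculates mean straining for an interval as "the sum of the straining values for the interval divided by the number of BMs recorded within the interval". The change score is post-baseline minus baseline, where "baseline is the mean degree of straining recorded during the OIC confirmation period", so one formula serves both periods. The section adds: "Negative changes from baseline indicated improvement".

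Two separate collection rules feed the formula. Section 6.2.4 covers the denominator: "All BMs will be recorded in the diary each day as they occur". Section 6.2.6 covers the numerator: "The degree of straining with each BM will be recorded at the time of the BM and after the BSS". The answer options run from 1 (no straining) to "5=An extreme amount", so 0 is not a possible answer.

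The Bristol Stool Scale mean in section 10.2.1.4 is "divided by the number of days within the interval in which the data were collected". The pain NRS (10.1.2) and daily opioid dose (10.1.3) use the same restriction. Section 10.2.1.5 does not carry it.

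Section 11.2.2 summarizes straining by arm and as change from baseline, and lists it among the variables whose group differences are examined with t-tests.

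**The concern.** The formula is correct only if every recorded BM has a straining rating. The plan intends that, but does not say what to do when a rating is skipped. A programmer following the text would count the unrated BM in the denominator, which gives it a value better than the best answer on the scale.

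Skipped items are foreseeable. The diary is on paper, several questions follow each BM, and section 4.1 admits patients with a Palliative Performance score as low as 30%. No other rule in the documents repairs the calculation. The four-day minimum in section 10.2.1.1 applies only to weekly SBM frequency.

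What is at stake is one secondary efficacy variable: its period means, its change from baseline and its comparison between arms. Section 11.1 says the pilot should inform the effect size for a larger trial, so a distorted straining mean could be carried forward.

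**Working it through.** The documents report no straining figure, so there is none to reproduce. The check compares the formula as written with one that divides by rated BMs only.

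**Inputs.** From the documents: the formula and sign convention (10.2.1.5), the 1-5 scale with one planned rating per BM (6.2.6), and recording of all BMs (6.2.4). Assumed, because not given: the unrated share m, taken from 0% to 30%, and the ratings in the examples.

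**Formula.** Let R be the sum of the ratings given, r the number of rated BMs and u the number of recorded but unrated BMs, with m = u/(r + u).
- As written: R/(r + u) = (1 - m) × R/r.
- Rated BMs only: R/r.

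**Complete ratings.** Baseline 4, 4, 3, 4 gives 15/4 = 3.75. Treatment 3, 3, 4, 3, 3, 3, 4, 3 gives 26/8 = 3.25. The two rules agree.

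**One unrated BM.** Five BMs, four rated 4 and one unrated: as written 16/5 = 3.2; rated only 16/4 = 4.0. Here m = 0.2 and 0.8 × 4.0 = 3.2.

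**All BMs unrated.** As written, 0/5 = 0, below the scale minimum of 1. Under the rated-only rule the mean is undefined and should be missing.

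**Change from baseline.** As written, the change is (1 - m_t) × μ_t - (1 - m_b) × μ_b, where t is treatment, b is baseline and μ is the mean of the rated BMs. The first two columns take every rating as 3 with no true change. The third takes a true fall from 3.5 to 2.5.

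| Unrated share | After baseline only | At baseline only | Equal in both periods, true change -1.0 |
|---|---|---|---|
| 10% | 2.7 - 3.0 = -0.3 | 3.0 - 2.7 = +0.3 | 0.9 × (-1.0) = -0.9 |
| 20% | 2.4 - 3.0 = -0.6 | 3.0 - 2.4 = +0.6 | 0.8 × (-1.0) = -0.8 |
| 30% | 2.1 - 3.0 = -0.9 | 3.0 - 2.1 = +0.9 | 0.7 × (-1.0) = -0.7 |

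Dividing by rated BMs gives 0.0 throughout the first two columns and -1.0 throughout the third.

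**Between arms.** Suppose the rated mean is 3 in both arms. With 20% unrated in one arm and 10% in the other, the treatment-period means are 2.4 and 2.7, a false difference of -0.3 in favour of the arm with more unrated BMs. With 10% unrated in both arms, both means are 2.7 and the difference is 0.

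**BMs or days not recorded at all.** These leave both numerator and denominator. Eight recorded BMs all rated 3 give 24/8 = 3.0, however many others went unrecorded. The error arises only for a BM that is recorded but not rated.

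**The case against.** The strongest reply is that the plan calls for one rating per BM, which makes the number of recorded BMs equal to the number of ratings. The phrase may simply be loose wording for rated BMs. Diaries are also reviewed for completeness at visits (6.1, 3.2.3, 3.2.4), diary compliance is assessed at each visit (5.6), and queries are raised for missing data (9.2). These steps should keep the unrated share down, and with complete ratings the formula is right. They do not define the calculation when a rating is still missing after review, so the written rule remains wrong in that case.

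The contrast with neighbouring formulas also has limits. The restricted ones are day-based, whereas straining is per BM. Sections 10.2.1.3 and 10.2.1.6 divide by all days in the period. Straining therefore does not break a uniform convention, and the case rests on the impossible score of 0.

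A reader might infer that missing answers always count as improvement, or that the rule favours naloxegol. The documents do not support either. The same formula produces the baseline, so ratings missing there make the change look worse, and equal shares understate a true improvement. A reader might also infer more skipping on treatment because of the baseline requirement: "A minimum of 7 days of diary data must have been recorded before the patient can be randomized for the study". That requirement concerns days of diary data, not a straining answer for each BM, and treatment diaries are reviewed too. Nothing in the documents indicates that skipping would differ between blinded arms. A false-positive rate for the t-test could be obtained only by supplying unrated shares, SDs and BM counts that the plan does not give.

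**Conclusion.** The definition is wrong as written, but the point is minor. Whenever a recorded BM lacks a straining rating, the interval mean is too low by the factor (1 - m). That result is algebraic and needs no assumption about why ratings are missing.

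The consequence for the change score has no fixed direction: false improvement if ratings are missing after baseline, false worsening if they are missing at baseline, and a shrunken change if the shares are equal. A false arm difference requires unrated shares that differ by arm. The figures of 0.3 to 0.9 points rest on an assumed 10% to 30% unrated and a constant rating of 3; the true share could be close to zero. The responder definition does not use straining.

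**What to change.** In section 10.2.1.5, define the denominator as the number of BMs in the interval that have a non-missing straining rating, and apply this to baseline and to treatment. State that the mean is missing when an interval has no rated BM. Report the percentage of recorded BMs without a straining rating by arm and period, so that readers can judge how complete the variable is.

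The cost is one phrase in the definition, one line of programming and one extra summary row. No new data are needed, and if every BM is rated the results do not change.

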#### **10.2.1.6 Days with complete evacuation**

For each BM, the patient will record in the diary whether or not they had complete evacuation (ie, no stool in their rectum that they could not empty out). The percentage of days with complete evacuation will be calculated as the number of days with complete evacuation within

the interval of interest divided by the total number of days in the interval, multiplied by 100. The percentage of days with complete evacuation will be calculated.

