## 5.5 Concomitant and post-study treatment(s)

It is recognized that some patients may have their pain managed by personal physicians who are not connected with the study. In these cases, the investigator should notify the patient's personal physicians of the patient's participation in the study, and to ask the physician to notify the study investigator should a change in their pain control regimen be made.

Concomitant non-opioid analgesics will not be prohibited, but investigators will be encouraged to maintain such drugs at stable doses on-study if possible.

Contraceptives (eg, oral contraceptive, implant, dermal contraception, long-term injectable contraceptive, intrauterine device) are allowed.

Patients who were on a maintenance bowel regimen (i.e. regular daily schedule) are allowed to continue on that regimen for the duration of the study. Patients who use laxatives on as needed basis (or those who do not use laxatives) will be required to stop all laxatives and other bowel regimens at randomization for the duration of the study. Bisacodyl will be provided at visit 2 for use during the study. During all treatment periods of the study if after a minimum of 48 hours the patient has not experienced a bowel movement they may take bisacodyl rescue therapy (10 to 15 mg dose). However, in the case the patient is unable to wait 48 hours to receive rescue laxative, rescue laxatives may be administered sooner than 48 hours at the discretion of the investigator. If the patient remains constipated, bisacodyl rescue therapy may be repeated up to 2 additional times, as necessary, each 10 to 15 mg doses administered at 12-hour intervals, or the investigator may prescribe a one-time use of an enema. The timing and administration of any rescue therapy used will be noted and recorded in the diary.

Patients will be instructed on the guidelines for rescue bisacodyl use. Patients will be asked to return unused bisacodyl at each subsequent visit. Documentation of bisacodyl use will be reviewed with the patient at each visit by comparing returned bisacodyl with diary records. If there is a discrepancy, the patient will be counseled regarding proper documentation of bisacodyl use in the diary.

Patients will be asked to record their daily opioid breakthrough medication use in the paper diary. Changes in the opioid regimen and laxative regimen may occur at the discretion of the investigator to ensure appropriate symptom management throughout the study.

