### **6.2.5      Stool consistency (Bristol Stool Scale - BSS)**

Patients will rate stool consistency through completion of the BSS after each BM. The BSS is a medical aid designed to classify the form of human feces into 7 categories. It was developed by Heaton at the University of Bristol and was first published in the Scandinavian Journal of Gastroenterology in 1997 [12]. The form of the stool depends on the time it spends in the colon. The 7 stool types are:

1. Separate hard lumps, like nuts (hard to pass)
2. Sausage-shaped, but lumpy
3. Like sausage, but with cracks on its surface
4. Like a sausage or snake, smooth and soft
5. Soft blobs with clear cut edges (passed easily)
6. Fluffy pieces with ragged edges, a mushy stool
7. Watery, no solid pieces.

Types 1 and 2 indicate constipation, Types 3 and 4 represent "ideal stools," and Types 5 to 7 are tending towards diarrhea or urgency.

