##### **10.2.1.1 SBMs Responder Rate**

A SBM is defined as a BM without rescue laxatives in the previous 24 hours. Days with no BMs should be recorded as zero, rather than missing. This diary data will be used to identify SBMs. The weekly SBM frequency within each time period will be calculated for each patient as:

(Total number of SBMs during the time period of interest/number of days) x 7,

where the denominator is the number of days during the time period in which the patient records data. If less than 4 days of data are recorded within a particular week, the data for that week will be considered insufficient and the rate will be set to missing for that week.

A responder is a patient with  $\geq 3$  SBM in a week and at least one SBM/week increase over baseline for the two weeks during which the study drug is taken. For the purposes of the analysis, the proportion of responders will be evaluated during the randomized period, and also during the extension period. The randomized period permits a comparison of response rates for those who received naloxegol and those who received placebo. The responder rate during the extension period for those patients who entered the extension period after having had placebo will be evaluated as supportive of the response rate determined during the randomized period.

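### Days with complete evacuation include stools that follow rescue, which inflates the score most in the arm using more rescue; stool form and straining include them too, with a less certain direction

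*Combined protocol and SAP*

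**What the plan says.** All places are in the combined protocol and SAP.

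- **Complete evacuation (10.2.1.6).** The record is made per BM: "For each BM, the patient will record in the diary whether or not they had complete evacuation". Days with complete evacuation are then "divided by the total number of days in the interval, multiplied by 100".
- **Straining (10.2.1.5).** The mean is "the sum of the straining values for the interval divided by the number of BMs recorded within the interval".
- **Stool form (10.2.1.4, 6.2.5).** The rating is made per BM: "Patients will rate stool consistency through completion of the BSS after each BM". The mean is the "sum of daily values for the interval divided by the number of days within the interval in which the data were collected". A rise from baseline is read as improvement.
- **Frequency endpoints (10.2.1.1 to 10.2.1.3).** These use SBMs: "A SBM is defined as a BM without rescue laxatives in the previous 24 hours".
- **Rescue (5.5).** In all treatment periods, once 48 hours have passed and "the patient has not experienced a bowel movement they may take bisacodyl rescue therapy". It may be given sooner at the investigator's discretion, repeated, or followed by a one-time enema. Timing goes in the diary. Under 6.2.9, rescue other than bisacodyl goes on the concomitant medication page.
- **Analysis (11.2.2).** Stool form, straining and complete evacuation are summarised by arm, and group differences are then to be tested with t-tests. Rescue doses, enemas and disimpactions per week are separate endpoints (10.2.1.9).

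**The concern.** The plan holds rescue-related BMs out of its frequency endpoints but not out of these three. Rescue depends on the outcome: a patient qualifies by going 48 hours without a BM. If naloxegol works, placebo patients will qualify more often, so more of their recorded BMs will have followed a stimulant laxative or an enema. Study bisacodyl is first supplied at Visit 2, so the change from baseline also mixes in BMs from a product that was not supplied during the baseline week.

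At stake is the size of the between-arm difference on constipation symptoms, a stated secondary objective (2.2). Section 11.1 wants the efficacy effect size in order to design a larger trial, and a diluted estimate could carry forward into that design.

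**Working it through.** The documents give no figure for these endpoints, so there is none to reproduce. The check has two parts: what the formulas imply, and an illustration in which every rate is an assumption.

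**1. Complete-evacuation days: direction from the formula.** Score = 100 × (days with complete evacuation) / (all days). The denominator does not change with rescue. If a day counts when at least one BM was complete, adding a complete rescue BM either leaves the count alone or raises it by one day. Section 10.2.1.6 does not say how a day with both a complete and an incomplete BM is scored, so this rests on the at-least-one reading.

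**2. Complete-evacuation days: illustration.** Assumed: 14 days; at most one BM a day; daily chance of a spontaneous BM 0.20 on placebo and 0.45 on naloxegol; rescue after two days without a BM, effective 90% of the time; 40% of SBMs complete in both arms. A simulation of 40,000 patients per arm gave, per week:

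| | SBMs | Rescue BMs |
|---|---|---|
| Placebo | 1.04 | 1.63 |
| Naloxegol | 2.65 | 1.01 |

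SBM-only difference: 100 × 0.40 × (2.65 − 1.04)/7 = 9.2 points.

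If a share c of rescue BMs is complete, counting all BMs removes 100 × c × (1.63 − 1.01)/7 = 8.86c points:

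| c | Removed | Remaining | Simulated |
|---|---|---|---|
| 30% | 2.7 | 6.5 | 6.5 |
| 50% | 4.4 | 4.8 | 4.8 |
| 70% | 6.2 | 3.0 | 2.9 |

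The simulated loss runs from about 30% (1 − 6.5/9.25) to 68% (1 − 2.93/9.21) of the SBM-only difference. Naloxegol stays ahead throughout.

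**3. What the 9.2 points measure.** Completeness per SBM was set equal in the two arms, so here the whole SBM-only difference is stool frequency. Under other assumed inputs (4 v 2 SBMs per week, 40% v 30% complete), complete SBMs per week are 4 × 0.40 = 1.6 and 2 × 0.30 = 0.6, a gap of 1.0. With equal completeness the gap would be 2 × 0.30 = 0.6 or 2 × 0.40 = 0.8, so frequency accounts for 60% to 80%.

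**4. Stool form and straining: direction not fixed.** Both are means. The share of BMs that follow rescue is 1.63/(1.04 + 1.63) = 0.610 on placebo and 1.01/(2.65 + 1.01) = 0.276 on naloxegol. With no true difference between arms on SBMs, the artefact (naloxegol minus placebo) is (rescue score − SBM score) × (0.276 − 0.610).

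- Straining, SBM mean assumed 3.0: rescue BMs at 2.0, 2.5 and 3.5 give about +0.33, +0.17 and −0.17. Higher is worse, so the first two favour placebo and the third favours naloxegol.
- Stool form, SBM mean assumed 2.5: rescue BMs at 5, 4 and 3 give −0.84, −0.50 and −0.17, all favouring placebo.

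For stool form the direction is plausible. Section 10.2.1.4 counts any rise as improvement, although 6.2.5 describes types 5 to 7 as tending toward diarrhea, and 1.1 lists diarrhea among the side effects of constipation treatments. For straining, the documents do not say whether rescue stools pass more easily.

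**The case against.** The best defence is that counting all BMs answers a legitimate question: how the bowel functions under each treatment with permitted rescue. Rescue use is reported by arm beside these scores, so a reader can see an imbalance. The responder and 24-hour laxation comparisons are already SBM-based. These are secondary endpoints in a pilot whose primary aim is safety, and attenuation is conservative for an efficacy claim. All of this stands, except that the plan does not label the measures as including rescue.

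A second objection concerns the remedy. SBM-only means of straining and stool form condition on an event after randomization. A patient with no SBM on treatment has no value; one with no SBM in the 7-day baseline has no change score. Fewer than 3 SBMs per week is one of the entry symptoms in 4.1, so such patients are to be expected, and if the drug works the on-treatment loss would fall mainly on placebo. This stands, and is why SBM-only means should not replace the all-BM means. It does not touch complete-evacuation days, where the denominator remains all days and nobody is dropped.

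A reader might go further and infer that all three endpoints credit the high-rescue arm with better bowel function, or that a real benefit is masked. The documents do not support that. They give no scores for rescue stools, the straining artefact can reverse, and inflation relative to spontaneous function does not put placebo ahead. Nor should higher power for an SBM-only version be read as recovered information on stool quality, since much of that contrast is frequency.

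**Conclusion.** The point holds for complete-evacuation days. Given the at-least-one reading of a complete day, including rescue BMs can only raise the score. It shrinks the tested difference if placebo patients have more complete-evacuation days that are due only to rescue. The fall from about 9 points to between 6.5 and 3 illustrates the mechanism on assumed rates; it is not an estimate for this trial.

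For stool form, bias toward the high-rescue arm is plausible but depends on rescue stools being looser than SBMs. For straining the direction is open. The responder analysis is not affected. This is a worthwhile clarification of secondary endpoints, not a threat to the trial's main conclusions.

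**What to change.** 1. **10.2.1.6.** Add the percentage of days with a complete SBM, meaning a complete BM with no rescue laxative or enema in the previous 24 hours. Include rescue recorded on the concomitant medication page. Keep all days as the denominator. Report it beside the present measure, labelled 'regardless of rescue', and state how a day with both complete and incomplete BMs is scored.
2. **10.2.1.4 and 10.2.1.5.** Keep the all-BM means with the same label. Add SBM-only means as a sensitivity analysis, and report the number of patients per arm with no SBM at baseline or on treatment.
3. **Baseline flag.** State which laxatives count as rescue before Visit 2. The SBM note in 4.1 differs from 10.2.1.1, bisacodyl is not yet supplied, and as-needed laxatives stop only at randomization.

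The cost is a little derivation work, since BM times and rescue timing are already collected. The drawback is that the complete-SBM-days measure partly overlaps with SBM frequency, so the two should not be presented as independent evidence.
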